### **2.3 Randomized Trials with IL-2**

Other regimens involving lower doses of IL-2 with and without interferon (IFN) have been reported to produce similar response rates to those observed with high dose (HD) IL-2, but these results have not been reproducible and the quality of responses has been less impressive (9,13,14). Before accepting lower dose regimens as equivalent to HD IL-2, it was imperative to establish that the quality of tumor responses with lower dose regimens was not inferior. Three large-scale randomized trials have now been completed that provide clinicians with useful insights into the relative merits of these various regimens and thus the optimal management of patients with metastatic renal cell carcinoma.

Investigators in France conducted a large-scale, phase III randomized trial comparing intermediate-dose IL-2 administered by continuous intravenous infusion plus subcutaneous IFN $\alpha$  with either IL-2 or IFN $\alpha$  administered alone (9). Four hundred twenty-five patients were enrolled. The three treatment groups were well balanced for age and gender as well as known predictors of response and survival. The response rate and 1-year event-free survival were significantly greater for the combined IL-2 and IFN $\alpha$  arm than for either of the single-agent arms, although there was no significant difference in overall survival among the three groups. Of note, responses were seen in only 6.5% and 7.5% of patients receiving IL-2 or IFN $\alpha$  alone, respectively, with only 2.9% and 6.1% of these patients still responding at the week 25 evaluation. Although more anti-tumor activity was seen with the combination arm, this was largely due to the rather limited activity of the single-agent regimens. How an intermediate-dose combination of IL-2 and IFN $\alpha$  would compare with high-dose IL-2 alone remained to be established.

The NCI Surgery Branch investigators performed a randomized trial comparing standard HD IL-2 and the intermediate dose (low dose – LD) intravenous bolus IL-2 regimen (LD IV IL-2) (15). After randomizing 117 patients, a third arm was added involving subcutaneous IL-2 administered in a fashion similar to that previously described by Sleijfer *et al.* Results were analyzed and reported according to groups that were concurrently randomized. Among the 306 patients concurrently assigned to either HD or LD IV IL-2, the response rate was significantly higher with high-dose therapy (21 versus 13 percent), with a trend towards more durable responses. Response durability and survival in complete responders was superior in patients who received the HD intravenous IL-2 compared to those who received the LD IV IL-2. There were no differences in overall survival. Although toxicities were also significantly greater in the high dose group (particularly hypotension), there were no deaths attributable to IL-2 in either arm and patient assessments of quality of life were found to be roughly equivalent. Among the patients concurrently assigned to either subcutaneous IL-2 or HD intravenous bolus IL-2, a higher response rate was seen with HD IL-2 (21 versus 10 percent) but the difference was of borderline statistical significance. Once again there were no differences in overall survival.

In an effort to determine the value of outpatient subcutaneous IL-2 and IFN $\alpha$  relative to high dose IL-2, the Cytokine Working Group performed a phase III trial in which patients were randomized to receive either outpatient IL-2 (5 MIU/m^2 subcutaneously every 8 hours x 3 doses on day 1 then daily 5 days/week for 4 weeks) and IFN $\alpha$  (5 MIU/m^2 subcutaneously thrice weekly for 4 weeks) every 6 weeks or standard high dose inpatient IL-2 (600,000 IU/kg/dose every 8 hours intravenously, days 1-5 and 15-19 [max 28 doses]) every 12 weeks (16). One hundred and ninety three patients were enrolled and 192 were evaluable. Patients were stratified for bone or liver metastases, primary in place and performance status 0/1 and the treatment arms were evenly balanced for these characteristics as well as other factors. 45% of patients had bone or liver metastases, 31% had primary in place and 60% were PS 0. Toxicities seen were typical for these regimens, including one treatment related death from progressive disease and ARDS on IL-2 and IFN arm and one death from capillary leak syndrome on high dose IL-2.

The response rate for high-dose IL-2 was 23% (22/95) versus 10% (9/91) for IL-2/IFN (p=0.018). Eight patients achieved a complete response on high dose IL-2 versus only 3 on low dose IL-2/IFN. The median response durations were 24 months for high dose IL-2 and 15 months for IL-2/IFN (p=0.18). Median overall survivals were 17 and 13 months (p=0.21), favoring high dose IL-2. Ten patients on high dose IL-2 were progression free at 3 years versus 3 on IL-2/IFN (p=0.08). Durable CRs favored HD IL-2 (7 vs. 0). Median progression free survival was 3 months for each

treatment arm. Of note, responses to high dose IL-2 were seen with equal frequency across the stratification criteria, while low dose IL-2/IFN appeared to produce fewer responses in patients with liver and/or bone metastases and in those who had not undergone prior nephrectomy to remove the primary tumor. For patients with bone or liver metastases ( $p=0.001$ ) or primary in place ( $p=0.04$ ) survival was superior with high dose IL-2 compared to IL-2/IFN, while no significant survival differences between the two treatments were noted for patients who had undergone prior nephrectomy or were without bone or liver metastases. Moreover, patients who had undergone a recent nephrectomy (debulking nephrectomy in the setting of stage IV disease) appeared to fare as well with IL-2/IFN as with HD IL-2.

Taken together these studies suggest that HD bolus IL-2 is superior in terms of response rate and response quality to regimens involving either low dose IL-2 and IFN or intermediate or low dose IL-2 or subcutaneous IFN. Furthermore, the benefit of high dose IL-2 relative to the lower dose regimens may be most pronounced in patients with unresected primary tumors or bone and/or liver metastases. This suggests that high dose IL-2 is required to produce responses in typically refractory sites and to eliminate the last tumor cell. This data suggests that high dose IL-2 should remain the preferred therapy for appropriately selected patients with access to such therapy. However, given the toxicity and limited efficacy of high dose IL-2 therapy, additional efforts should be directed at better defining the patient population for whom this therapy is appropriate and finding means to ameliorate toxicity and increase efficacy.

## **2.4 Predictors of Clinical Benefit from Cytokine-Based Therapy**

Many groups have attempted to determine reliable predictors of response and survival for patients with metastatic renal cell carcinoma who were receiving immunotherapy. Factors that have been variably associated with response include performance status, number of organs with metastases (one versus two or more), absence of bone metastases, prior nephrectomy, degree of treatment-related thrombocytopenia, absence of prior interferon therapy, thyroid dysfunction, rebound lymphocytosis, erythropoietin production, and post-treatment elevations of blood TNF- $\alpha$  and IL-1 levels (17-20).

Motzer and colleagues have shown in patients receiving IFN that poor survival is associated with low Karnofsky performance status, high serum lactate dehydrogenase, low hemoglobin, high “corrected” serum calcium and time from initial renal cell carcinoma diagnosis to start of therapy of less than one year (20). In a cohort of 453 patients who received IFN as initial therapy, the median survival for the favorable (no risk factors), intermediate (one or two risk factors) and poor (three or more risk factors) risk groups were 30, 14 and 5 months respectively. Negrier and associates also identified independent predictors of rapid disease progression, defined as progression within 10 weeks of initiation of therapy (19, 21). These included greater than one metastatic site, disease-free interval of less than 1 year, and presence of liver metastases or mediastinal nodes, as well as type of immunotherapy used. Patients with liver metastases, more than one site of disease, and disease-free interval of less than 1 year had a lower response rate and a median survival of only 6 months, even while receiving combination IL-2 and interferon  $\alpha$  therapy. Figlin and colleagues identified prior nephrectomy and time from nephrectomy to relapse as important predictors of survival in patients receiving IL-2-based therapy (10). In their series, patients who received systemic immunotherapy for metastatic disease more than 6 months after nephrectomy had the best median survival and had a 3-year survival rate of 46%. A recent multivariate analysis by the same group of investigators that was confined to patients who received IL-2 after nephrectomy revealed survival to be inversely

associated with lymph node involvement, constitutional symptoms, sarcomatoid histology, metastases involving sites other than bone or lung or multiple sites, and a TSH level > 2.0 mIU/L (10). They proposed a scoring algorithm based on these features in which survival at one year was predicted to vary from 1- 92%. Recent data from the Cytokine Working Group phase III trial, mentioned above, suggested that disease site factors such as primary in place or hepatic or bone metastases may be more predictive of a poor response to low dose IL-2 and IFN regimens, than to high dose IL-2. Furthermore, this study suggested the greatest benefit from high dose IL-2 relative to lower dose regimens might be seen in patients with primaries in place and/or liver and bone metastases. These data call into question some of the prior studies and suggests that additional predictors of response and survival in patients receiving cytokine-based immunotherapy are necessary.

## **2.5 Influence of subtype on response to IL-2**

Responses to immunotherapy are most frequently seen in patients with renal cell carcinoma of clear cell histology. This observation was recently detailed in a retrospective analysis by Upton et al of pathology specimens obtained from 231 patients who had received IL-2 therapy on Cytokine Working Group clinical trials (22). For patients with tumor specimens available for review, the response rate to IL-2 was 21 percent (30 of 146) for patients with clear cell histology primary tumors, compared to 6 percent for patients with non-clear cell histology (1 responder in 17 patients). Among the patients with clear cell cancer in their kidney specimen, response to IL-2 was also associated with the presence of > 50% alveolar features, no papillary features or granular features in the pathologic material. The response rate was 39 percent (14 of 36) in patients with all these features. In addition, patients with clear cell tumors with < 50% alveolar or granular features but no papillary features in the specimen had a response rate of 19 percent (15 of 77) compared to 3 percent (1 of 33) in the other patients.

From this data, a model was developed that placed patients with clear cell cancers into good, intermediate and poor response categories based on the analysis of their primary tumors.

When this model was then applied to the 68 patients with specimens from other metastatic sites, all 7 tumor responses were seen in the 42 patients with clear cell cancer and intermediate or good prognostic features, thus confirming the validity of the model developed from the primary kidney tumor specimens. In addition, median survivals for all patients with clear cell tumors by risk group were 2.87, 1.36 and 0.87 years, respectively ( $p < 0.001$ ), indicating that the model may have prognostic as well as predictive value.

**Table 1. Histologic Predictors of Response to IL-2 Therapy**

Category	Pathology Type	N	Response	RR %
Good	Clear Cell Alveolar > 50% No granular No papillary	36	14	39
Intermediate	Clear Cell Alveolar <50% Granular <50% No papillary	77	15	19
Poor	Others	33	1	3

As a result of these data, it has been conjectured that patients with non-clear cell histology and those with clear cell histology but adverse pathologic features (papillary and/or no alveolar features, and/or >50 percent granular features) receive alternative non-immunotherapy-based treatments; however, this supposition requires confirmation using an independent data set. In addition, the encouraging results in the favorable pathology types require prospective confirmation to determine the true response rates in a selected population. The association of response with pathologic features suggests that more intensive evaluation of tumor tissue might yield more robust predictors of response. Given that even in the most favorable prognostic group only 39% of patients responded to IL-2 therapy, additional investigations into tumor-associated predictors of responsiveness to IL-2 are still warranted.

## 2.6 Molecular Markers of Response to IL-2

Some investigators have begun to examine tumor tissue to identify molecular markers that might predict the outcome of patients with renal cell carcinoma. Recently, carbonic anhydrase IX (CAIX) has been identified as one potential marker (23). CAIX is thought to play a role in cell proliferation in response to hypoxic conditions. CAIX expression is mediated by the HIF-1 alpha transcriptional complex and induced in many tumors types, but is absent in most normal tissue with the exception of epithelial cells of the gastric mucosa. Bui *et al* used a monoclonal antibody designed to detect CAIX expression to perform an immunohistochemical analysis of paraffin embedded renal cell carcinoma specimens (23). They showed that > 90% of renal cell carcinomas express CAIX and that its expression decreases with advancing stage. In their analysis, high CAIX expression in primary tumors was seen in 79% of patients and was associated with improved survival and, possibly, response to IL-2-based therapy. In addition, all long-term responders to IL-2-based treatment had high CAIX expression. In this study, low CAIX expression was associated with a worse outcome for patients with locally advanced renal cell carcinoma and was an independent predictor of outcome in patients with metastatic disease.

Building on this work, Atkins *et al* performed a nested case-control study within the larger Upton pathology cohort (24). Paraffin-embedded tissue sections of RCC were obtained from patients who had previously been included in the pathology review and were immunostained with the same CAIX antibody used by Bui *et al*. CAIX expression levels were correlated with type of IL-2 treatment, response to IL-2, pathologic risk categorization and survival. As in the report by Bui *et al*, the percentage of CAIX positive tumor cells was utilized to separate high (> 85%) and low ( $\leq$  85%) expressors. Tissue specimens were obtained from 66 patients. Twenty-seven of the selected patients (41%) achieved a response (10CR/17PR) to high-dose IL-2 (32) or low-dose IL-2-based

(34) regimens with 20 (30%) remaining alive at a median follow-up of 2.6 years. Fifty-eight specimens were assessed as clear cell, with 56, 33 and 4 having alveolar, granular and papillary features, respectively. Twenty-four (36%), 31 (47%) and 11 (17%) were classified into good, intermediate, or high-risk groups according to the pathology model created by Upton *et al* that is described above. Forty-one specimens (62%) had high CAIX expression. Twenty-one of 27 (78%) responding patients had high CAIX expression, compared to 20/39 (51%) of non-responders (OR=3.3, p=0.04). A similar survival benefit was observed (p=0.04). Median survival was 3 and 1 years for high and low CAIX expressers, respectively. Survival greater than 5 years was only seen in the high CAIX expressing group. High CAIX staining was associated with better pathology prognosis and, when stratified by group, the odds ratios of CAIX expression were unequal across groups. The strongest association was in the intermediate pathology group where 9/9 responders had high CAIX expression vs. 11/22 non-responders, suggesting a possible refinement of the Upton pathology model. A resultant group with good pathology or intermediate pathology and high CAIX expression contained 26 of 27 (96%) responders compared to only 18/39 (46%) non-responders (OR = 30; p <0.01). Survival benefit was also seen (p< 0.01). The authors concluded that based on this data, patients with low CAIX staining and intermediate or poor risk pathology classification should be considered for non-IL-2 based treatments.

**Table 2. CAIX Staining and Response Rate**

Category	N	Response Rate %
Low CAIX staining Intermediate or poor path	22	<5%
Other	44	59%

While this model requires validation, it is possible that IL-2 therapy could ultimately be reserved for patients with favorable or intermediate pathology classification and high CAIX staining who appear to be more likely to benefit.

Additional studies to explain these preliminary observations and correlate results with pathologic features, sites of disease and previously described clinical features are necessary. In addition, gene expression profiling of tumor specimens to identify new proteins or patterns of gene expression that might be associated with IL-2 responsiveness may eventually help narrow the application of IL-2 therapy to those who will benefit the most. The SELECT Cytokine Working Group has recently concluded that combined histologic subtype and CAIX predictors were unable to define a predictor of response (McDermott et al, 2017; 150).

## **2.8 Autophagy serves as a survival pathway for stressed tumor cells enhancing survival following cytotoxic chemotherapy.**

Autophagy is an important highly evolutionarily conserved catabolic process by which cells shuttle effete or damaged organelles and proteins to the autophagosome for sequestration and destruction. In addition to its homeostatic role, the autophagic process also allows cells to survive periods of nutrient deprivation and stress. Autophagy is thought to maintain cellular metabolism through increased turnover of cell components during times of nutrient deprivation. A growing body of literature suggests that autophagy is in fact a form of programmed cell survival and is induced to prevent apoptosis or necrosis (29-31). As is the case in normal cells, autophagy is induced in tumor cells during times of metabolic stress. In fact, several studies have demonstrated that markers of increased autophagic flux localize to metabolically stressed areas of tumor (32). In particular, a recent study by Fujii et al. examined 71 resected adenocarcinomas and demonstrated a high correlation between worse prognosis and increased levels of autophagy in the specimens (33). That autophagy can protect tumor cells during times of stress has led to increased interest in blocking this process as a means of anti-tumor therapy. Inhibition of autophagy as a single agent is unlikely to have much clinical impact since only a small fraction of the tumor cells are under metabolic stress at any given time. Therefore, most strategies have focused on the combination of autophagy inhibition in combination with agents that induce cellular stress (34, 35). Most modern neoplastic therapies fall into this category inducing cellular stress either by genotoxic injury, metabolic insult or blockade of growth factor activity. As shown in **Figure 1**, administration of chloroquine, an inhibitor of autophagy at 50mg/kg/d limits the weight gain in mice observed with high dose IL-2 administration [6x10^5 IU bid x 5D] concurrent with administration.

**Figure 1. Chloroquine limits IL-2 Induced Vascular Leak and Weight Gain. Weight gain observed with IL-2 administration was ameliorated with chloroquine coadministration.** Shown in the ordinate/y axis is the change in weight for each animal over the days of treatment. IL-2+CQ versus IL-2, Days 3 and 6;  $p=0.04$

[figure not shown]

## 2.9 Chloroquine and its derivatives inhibit autophagy and enhance immunotherapy and chemotherapy effects.

Chloroquine (CQ) is a synthetic 4-aminoquinoline that has been used for 60 years in humans initially for malaria prophylaxis and treatment, and with emergence of resistance, in patients with systemic lupus erythematosus, rheumatoid arthritis, and human immunodeficiency virus (HIV). It is an inexpensive orally available drug with a large therapeutic index. Chloroquine derivatives such as HCQ are still used extensively in patients with rheumatoid arthritis and lupus erythematosus. Chloroquine blocks acidification of the lysosome, thus inhibiting the last step in autophagy. With this last step blocked, a cell reliant on autophagy will increase the generation of autophagosomes and will eventually undergo either apoptotic or non-apoptotic cell death. Evidence in mouse models and human cancer cell lines suggest CQ may have significant anti-tumor activity by inhibiting autophagy induced by cancer therapy (35). Hydroxychloroquine is generally considered the safest disease-modifying agent currently used to treat rheumatic diseases. Up to 10% of patients will experience nausea, headache, or bizarre dreams, but these are infrequently dose-limiting. Retinal toxicity is a rare complication, estimated to occur in <1% of patients treated for years at doses not exceeding 6.5 mg/kg/day lean body weight, or approximately 400 mg/day (36, 37). Given the prolonged half-life of this drug ( $t_{1/2}=40=45$  d), treatment with daily doses of up to 1200 mg daily for a maximum of one month would achieve plasma concentrations approximating steady state with 400 mg daily dosing, and the risk of retinal toxicity for this relatively short-term exposure is thus low. While data is sparse regarding precise risk at higher daily dosing, Shearer and Dubois reported only a single patient with retinopathy in a survey of 94 patients treated with HCQ 800 mg daily for up to 54 months (38). Levy et al. identified 78 patients receiving a daily dosage  $>7.8$  mg/kg, and of the 3 with possible or definite retinal toxicity, HCQ was taken for at least 3.5 years (36). Because retinal toxicity may progress after drug cessation (39), HCQ will be discontinued in any patients reporting any visual complaints. A formal

ophthalmic evaluation plus a 3 month follow-up examination will be obtained only with ocular symptoms.

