#### **6.3.2.5 Toxicities**

Abdominal pain, alopecia, anemia, angina, anorexia, anuria, arthralgia, ascites, atrial fibrillation, azotemia, back pain, chills, cholestasis, conjunctivitis, constipation, diarrhea, drowsiness, dysgeusia, dyspepsia, dyspnea, dysuria, edema, elevated hepatic enzymes, eosinophilia, erythema, exfoliative dermatitis, fatigue, fever, GI bleeding, GI perforation, glomerulonephritis, hallucinations, headache, hematuria, hepatomegaly, hyperbilirubinemia, hyperkalemia, hypoalbuminemia, hypocalcemia, hypokalemia, hypomagnesemia, hyponatremia, hypophosphatemia, hypotension, hypovolemia, infection, injection site reaction, interstitial nephritis, jaundice, leukocytosis, leukopenia, lymphopenia, malaise, metabolic acidosis, metabolic alkalosis, myalgia, myocardial infarction, nausea/vomiting, oliguria, pancreatitis, paranoia, petechiae, pleural effusion, premature atrial contractions (PACs), premature ventricular contractions (PVCs), proteinuria, pruritus, pulmonary edema, purpura, sinus bradycardia, sinus tachycardia, splenomegaly, stomatitis, supraventricular tachycardia (SVT), syncope, tachypnea, thrombocytopenia, thrombosis, urticaria, visual impairment, weakness, weight gain, weight loss, wheezing, xerosis.

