### **6.4 Response Assessment/ Duration of Therapy**

Patients will undergo CT scans at week 8 and week 12 (+/- 1 week) following initiation of IL-2 therapy and then after each course (every 10-12 weeks). After the final course (week 36), patients will undergo CT scan evaluation every 12 weeks (+/- 2 weeks) for up to one year or until tumor progression (whichever comes first). If additional scans are performed for clinical reasons, the study schedule may be altered to perform the requisite scans at a more acceptable time point. The change in timing of study scans must be approved by the local PI and documented. For patients who have not shown progression at the end of one year, response will be captured during follow-up for survival (explained below).

Patients with evidence of tumor shrinkage with all lesions measurable and evaluable may receive up to 3 courses of IL-2 therapy. Course 2 will start on or within 2 weeks following day 85 and follow the same schedule as in Course 1. Course 3 can start within 2 weeks of completion of Course 2. Patients not receiving IL-2 during course 2 with tumor shrinkage by week 24 can receive a 2nd course of IL-2 beginning within 2 weeks of week 25.

Patients with no evidence of progression by RECIST 1.1 criteria may receive continued treatment with hydroxychloroquine through one year of initiation of HCQ treatment (Day -14) or until disease progression.

Tumor response will be assessed by the NCI’s Response Evaluation Criteria in Solid Tumors (RECIST) 1.1 guidelines. Patients will undergo tumor evaluation with physical exam and CT scans at week 8 (+/- 1 week) and week 12 (+/- 1 week), then after each course (every 10-12 weeks). After the final course (week 36), patients will undergo CT scan evaluation every 12 weeks (+/- 2 weeks) for up to one year or until tumor progression (whichever occurs first). If additional scans are performed for clinical reasons, the study schedule may be altered to perform the requisite scans at a more acceptable time point. The change in timing of study scans must be approved by the local PI and documented. For patients who have not shown progression at the end of one year, response will be captured during follow-up for survival, which will be done on all patients via telephone contact and medical record review. Patients with progressive disease by RECIST 1.1 criteria will be taken off study.

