## 9.2 Dose Modification for Toxicity: HD IL-2 and Hydroxychloroquine

Modification of the treatment protocol will occur by withholding doses of IL-2 rather than continuing therapy at a reduced dose. The only dose modification for patients of Hydroxychloroquine will be for those individuals deemed by the treating investigator as ‘likely’ due to hydroxychloroquine or the combination and not to IL-2 alone based on their experience and dose reduction as shown in **Table 5**. Missed doses of IL-2 will not be made up. Dose of IL-2 will be withheld for:

**9.2.1 Hypotension** refractory to fluids and pressors or requiring unacceptably high pressor doses (those associated with individual decrease in extremity perfusion). We will use vasopressors judiciously where necessary to support patients with limiting kidney/other organ perfusion. Requirement for vasopressors will be a relative indication for concluding a cycle (see 10.4.2.3 below).

**9.2.2 Anuria** for >24 hours and unresponsive to fluid replacement

**9.2.3 Respiratory distress** requiring oxygen >4 liters to maintain O2 saturation >95%.

**9.2.4 Confusion** (mental status changes can progress to paranoia despite discontinuation of IL-2; it is imperative that the IL-2 be stopped at any sign of persistent confusion or disorientation).

**9.2.5 Sustained ventricular tachycardia** or any sign or symptom of myocardial ischemia or myocarditis. Patients experiencing sustained ventricular tachycardia or myocardial ischemia should not receive further treatment with IL-2

**9.2.6 Metabolic acidosis** with HCO3 < 18, despite attempts to correct with IV HCO3.

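### Section 2.9 stops HCQ for any visual complaint, but the toxicity sections do not carry that rule and section 9.2 gives a different one

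*Combined protocol and SAP*

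**What the plan says.** **Stopping and reducing HCQ.** Section 2.9, a background section, notes that retinal toxicity can progress after the drug is stopped, and concludes that "HCQ will be discontinued in any patients reporting any visual complaints". It provides an eye examination, with a three-month repeat, only when there are ocular symptoms.

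Section 9.2 reads: "The only dose modification for patients of Hydroxychloroquine will be for those individuals deemed by the treating investigator" as having toxicity likely due to HCQ or the combination and not to IL-2 alone; the action is reduction under Table 5 (600 to 400 to 200 mg/d). Sections 6.3.1.1 and 9.4 also allow the two reduction steps, for treatment-limiting toxicity.

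**Visual effects.** Section 6.3.1.3 lists blurred vision, visual disturbance and retinopathy for HCQ. Section 6.3.2.5 lists "visual impairment" for IL-2.

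**Exposure.** Section 2.9 considers "daily doses of up to 1200 mg daily for a maximum of one month", argues that this brings drug levels close to those of long-term treatment at 400 mg/d, and concludes that "the risk of retinal toxicity for this relatively short-term exposure is thus low". Section 6.4 says that patients without progression "may receive continued treatment with hydroxychloroquine through one year of initiation of HCQ treatment (Day -14") or until progression. The Summary repeats this, but also says that HCQ runs until progression or until 12 weeks after a documented complete response.

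**The concern.** The instruction in 2.9 is mandatory and unconditional, yet it stands outside the sections a site consults when managing toxicity. The rule in those sections depends on attribution and leads to a different action. Visual symptoms are plausible with either drug, so attribution may be uncertain, particularly during an IL-2 week.

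The protocol itself says that early retinal changes are reversible but may progress despite discontinuation once advanced. No routine eye examination is scheduled in section 5.0 or Appendix B. After entry, action on symptoms is the only specific retinal safeguard, so the protocol should state that action once and clearly. In addition, the kinetic sentence supporting low retinal risk describes a much shorter course than the one the trial allows.

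**Working it through.** **1. The rules side by side**

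| Complaint attributed to | Under 2.9 | Under 9.2 (reduction steps also in 6.3.1.1 and 9.4) |
|---|---|---|
| HCQ or the combination | HCQ stopped | HCQ reduced to 400, then 200 mg/d |
| IL-2 alone | HCQ stopped | No HCQ change |

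The actions differ in both rows. Other places that could settle the matter:

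- Section 6.4.2 refers toxicity stops to 9.5. Its own general item is a change in the patient's condition, as judged by the investigator.
- Section 9.5 has 16 items, none of them ocular. Item 9.5.16 is a catch-all for severe or life-threatening toxicity in the investigator's opinion, so it does not implement a stop for any complaint.
- Appendix B schedules no eye examination, and the Appendix F patient instructions do not mention vision.

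**2. The kinetic sentence**

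Inputs: half-life T of 40 to 45 days and the 400 mg/d reference (2.9); 600 mg/d (Summary, Table 5); one year from Day -14 (6.4). The diary headed Day 267 to Day 351 agrees: 351 + 14 = 365 days. Assumptions: linear one-compartment kinetics, no loading dose, month = 30 days.

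Level relative to the 400 mg/d steady state: R = (dose/400) × (1 − 2^(−t/T)).

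- The plan's own case, 1200 mg/d for 30 days: 3 × (1 − 2^(−30/40)) = 1.22; with T = 45, 1.11. A month of 28 to 31 days gives 1.05 to 1.25. The statement holds for the case it describes.
- 600 mg/d reaches R = 1 when 2^(−t/T) = 1/3, so t = T × log2(3) = 63 days (T = 40) or 71 days (T = 45).
- 600 mg/d at 365 days: 1.5 × (1 − 2^(−365/T)) = 1.50 (T = 40) or 1.49 (T = 45).

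Cumulative dose: 1.2 × 30 = 36 g in the plan's case and 0.6 × 365 = 219 g in the trial, a ratio of 6.1.

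**3. The longer-term evidence that the protocol cites**

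- Section 2.9: 1 retinopathy in 94 patients on 800 mg/d for up to 54 months, or 1.1% (exact 95% CI 0.03 to 5.8%).
- Section 2.9: 3 possible or definite cases in 78 patients above 7.8 mg/kg/d, or 3.8% (0.8 to 10.8%), all after at least 3.5 years.
- Section 2.11: a 730 g benchmark, which equals 0.4 × 365 × 5. The trial's 219 g is 219/730 = 30% of it; at 600 mg/d it would take 730/0.6 = 1,217 days, about 3.3 years.
- The under-1% figure in 2.9 is for doses up to 6.5 mg/kg/d of lean weight. A dose of 600 mg exceeds that below 600/6.5 = 92 kg lean weight. Section 2.9 acknowledges that data at higher daily doses are sparse.

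**The case against.** The best defence is that 9.2 governs dose modification and 2.9 governs discontinuation, which are different acts. If the word only in 9.2 excluded every other way of ending HCQ, it would also clash with the stops for progression, pregnancy and intercurrent illness in 6.4.2. On this reading a visual complaint stops HCQ under 2.9, 9.2 is not engaged, and the fault is one of placement. This carries weight, especially for complaints attributed to IL-2, where 9.2 could simply be silent. It does not resolve complaints attributed to HCQ, for which 2.9 prescribes stopping and the operative sections provide reduction.

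Three stronger inferences are tempting, and the documents do not support them:

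- **That the whole retinal-safety case covers only one month.** Only the kinetic sentence does. The text that follows it, and 2.11, cite years of exposure, including at a higher dose.
- **That acting on symptoms is the only retinal safeguard.** Exclusion 3.2.xx keeps out patients with documented macular degeneration or diabetic retinopathy. The statement holds only for specific safeguards during treatment.
- **That sites will treat the same complaint differently.** The documents show that they could while each follows the protocol; they do not show that they will.

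One year is also a permitted maximum. Median PFS in the High Dose Aldesleukin Select trial was 4.3 months (section 2.2), so many patients may stop earlier. The 6.1-fold ratio is against a one-month scenario; against the protocol's own cumulative benchmark, exposure is well below.

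**Conclusion.** The point holds as an unreconciled safety instruction. The stop rule in 2.9 has no attribution condition and is absent from 6.4.2, 9.2, 9.4, 9.5 and Appendix B, while the rule in 9.2 is attribution-based and leads to reduction. This part rests on the text alone.

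The exposure point is secondary. The kinetic sentence does not describe a regimen that passes the 400 mg/d steady state after about 9 to 10 weeks and approaches 1.5 times that level by one year. This assumes linear one-compartment kinetics, the stated half-life and uninterrupted dosing at 600 mg/d. Given the cited longer-term data, it does not show that retinal risk in this trial is high, and restating it would not by itself change what the trial does.

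The inconsistency is worth correcting because it concerns safety and is cheap to remove. It falls short of an essential correction: the primary endpoint, sample size and analysis do not depend on it.

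**What to change.** - Reconcile 2.9, 6.3.1.1, 9.2, 9.4 and 9.5 so that a single rule for visual complaints, with its attribution condition stated, stands in the section sites use. The sponsor's clinical and safety team should decide which rule that is.
- Restate the kinetic sentence in 2.9 for the regimen given, 600 mg/d for up to one year. The longer-term citations can stay.
- Reconcile the two HCQ duration statements in the Summary. One has no calendar limit and the other ends at one year; they also differ after a complete response. Maximum exposure depends on which applies.

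The cost is protocol wording, with no added patients or visits. The exposure comparison in 2.9 will read less favourably than it does now.
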